7.6 Description of procedure

MRI

Imaging interventions: Once contraindications to magnetic resonance imaging are excluded by use of the facility's screening forms, the risks of undergoing a scan are minimal. A trained scanner operator or radiographer will go through a list of possible risks with the participant before scanning. The MRI scanner consists of a large powerful magnet. Magnetic resonance imaging uses no ionising radiation. There are, however, potential hazards associated with MRI and the scanning of participants including the presence of surgical implants, participants' clothing, jewellery (such as body piercings) bodily habitus, or medical conditions. A comprehensive list of potential risks has been compiled, and the participant should be checked against this by the operator, prior to entering the controlled areas of the MRI scanners. As per standard scanning procedure, participants will be invited to get changed into provided scrubs prior to scanning in order to minimise risk. During the actual scanning procedure, the scanner produces loud banging noises, and the participant will be given suitable hearing protection (earplugs – these will be fitted correctly). The participant will be attached to physiological monitors (i.e. pulse and respiration). Where necessary (i.e. in the case of glasses being removed), vision will be corrected using MR-compatible optical frames. There is a small mirror that will allow them to see out of the scanner. During the experiment, the participant will be able to communicate with the operator in the control room. In addition, they will be given a call button, which allows them to alert the operator at any time. People with a history of claustrophobia may be excluded from participation in the study. All participants will still be introduced carefully to the scanner and allowed to leave at any stage, should they wish to do so. Once in the scanner, participants will be able to indicate immediately if they wish the scanning to cease by pressing a call button in their hands.

Once the participant is comfortable to begin scanning, the radiographer will begin the relevant scan protocol which consists of different MR sequences aimed at imaging different structural and functional properties of the CNS before, during and after the application of different nociceptive stimuli. In some instances, participants will also be presented with innocuous 'control' sensations like visual stimuli (e.g.

flashing chequerboards, colourful images) or auditory stimuli (e.g. white noise) matched in terms of saliency to the painful stimuli.

Immediately following the scan session, the participant will be taken out of the scanner and led to an adjacent, private examination room so that they can change back into their own clothes.

Participants will be thanked and have a follow up visit booked prior to leaving.

The study intervention is online cognitive behavioural therapy for insomnia (CBT-I) through a commercially available programme, Sleepio. The programme involves 6 sessions of automated CBT-I with an automated, virtual professor and access to a daily online sleep diary. Participants may also interact with an online community and library of resources.

7.7 Discontinuation/Withdrawal of Participants from Study

Each participant has the right to withdraw from the study at any time. In addition, the Investigator may discontinue a participant from the study at any time if the Investigator considers it necessary for any reason including:

- Ineligibility (either arising during the study or retrospectively having been overlooked at screening)
- Significant protocol deviation
- Significant non-compliance with treatment regimen or study requirements
- Withdrawal of Consent
- Loss to follow up

Withdrawal from the study may result in exclusion of the data from that participant from analysis, if required by the participant.

The sample size for the study takes into account attrition over the course of the study and so withdrawn participants will not need to be directly replaced.

The reason for withdrawal will be recorded in the CRF.

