1. SYNOPSIS

Study Title	Characterisation of Pain in patients with musculoskeletal disease: a prospective, L ongitudinal, observational study with an E mbedded feasibility window of opportunity S leep S tudy (Pain-LESS)			
Internal ref. no. / short title	. Pain-LESS study			
Study Design	Prospective, longitudinal, cohort study digital CBT-I.	with embedded feasibility study of		
Study Participants	Patients with musculoskeletal disease			
Planned Sample Size	490 participants with rheumatoid arthri	tis		
	490 participants with fibromyalgia (of w feasibility study of dCBT-i.	hich 80 will be included in the		
Planned Study Period	April 15th 2019 to 30 th April 2025			
	Objectives	Outcome Measures		
Primary	To investigate whether patients with inflammatory arthritis and features of centrally driven pain have reduced chance of responding to treatment.	Primary outcome: Percentage achieving Disease Activity Score <2.6, 6 months after commencing anti-rheumatic treatment. Secondary outcome: Other measures include Disease Activity Score reduction of ≥1.2; simple disease activity score ≤3.3; Clinical Disease Activity Index ≤2.8; American College of Rheumatology (ACR)/European League Against Rheumatism (EULAR) Boolean (28 tender joint count, 28 swollen joint count, patient's global assessment (0−10 scale), CRP (mg/dL), all ≤1), modified DAPSA<4.		
Secondary	To describe the prevalence of centrally driven pain in patients with other musculoskeletal conditions.	Scoring according to: Central Sensitivity Inventory, Fibromyalgia survey criteria, PainDETECT questionnaire alongside neuroimaging findings.		
Secondary	To investigate whether digital CBT-I can improve quality of life and centrally driven symptoms in people with FM	SIQR, sleep actigraphy, online cognitive assessment at baseline, 12 weeks, and 24 weeks Neuroimaging at baseline and 12 weeks.		
	To determine barriers and facilitators to a definitive trial of digital CBT-I in people with FM	Focus group at 24 weeks		

	To evaluate the cost effectiveness of digital CBT-I	EQ-5D-5L Healthcare usage dairy

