9.2 Number of Participants

Previous work, using the ratio of tender to swollen joints as an indirect marker of central sensitization in patients with either RA or PSA, has shown that on average 43% of patients with low levels of likely central sensitization achieved remission (using DAS-28 remission criteria) compared to 23% in those with high levels of central sensitisation when being treated with either methotrexate or an anti-TNF agent. However a data simulation study showed that, for machine-learning methods, a sample size of 70 times the number of variables allows accurate identification of the data structure (36). Using the seven main variables of pain, fatigue, sleep disturbance, dyscognition, depression, anxiety and function, data for 490 participants, for each condition would be needed, including the feasibility study.

For the feasibility study 80 participants will be recruited in total, with 40 being assessed using MRI. Participants will be randomised on a 1:1 ratio to the intervention and standard care groups. This should provide a large enough sample to inform the practicalities of delivering dCBT-I, MRI assessments, and provide information on recruitment, uptake, and attrition, which will inform the design of the definitive trial. A moderate effect size (Cohen's d >0.3) would be sufficient to accept the result as worth investigating, in order to achieve a meaningful clinical benefit for patients, and in keeping with similar effects of CBT-I on cognitive outcomes in insomnia.

All participants in the Sleep sub-study will be invited to participate in the focus groups. However, it is envisioned that 18 (three groups of six participants) will take part, owing to the time commitment involved.

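### Section 7.7 of the protocol says the sample size allows for attrition, but the only derivation of 490 per condition is 70 x 7 and contains no allowance

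*Protocol*

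**What the plan says.** Protocol section 7.7 (Discontinuation/Withdrawal) says that "The sample size for the study takes into account attrition over the course of the study", and concludes that participants who withdraw need not be directly replaced. The same section adds: "Withdrawal from the study may result in exclusion of the data from that participant from analysis, if required by the participant".

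Protocol section 9.2 (Number of Participants) sizes the main study. It first cites remission rates of 43% and 23% for low and high central sensitisation, but calculates nothing from them. It then turns to a simulation study of machine-learning methods, in which "a sample size of 70 times the number of variables allows accurate identification of the data structure". The variables are listed: "Using the seven main variables of pain, fatigue, sleep disturbance, dyscognition, depression, anxiety and function". The conclusion is that "data for 490 participants, for each condition would be needed, including the feasibility study".

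The synopsis plans 490 participants with rheumatoid arthritis and 490 with fibromyalgia, the latter including the 80 in the feasibility study. Neither 7.7 nor 9.2 gives an attrition rate or an inflation step.

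**The concern.** Section 9.2 states how many participants must contribute data. The synopsis states how many will be recruited. If attrition had been allowed for, the second number would be larger than the first, but they are equal. The sentence in 7.7 therefore describes a margin that the derivation does not contain.

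The sentence also has a practical role, because it is the stated reason for not replacing withdrawals. An ethics committee or a reader of the results would take from it that 490 can lose participants and still meet its basis. The 70-per-variable rule is the only basis offered for 490. Section 5 expects participation of around 18 months, and 7.7 lists several routes by which participants may leave, so some loss is foreseeable.

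**Working it through.** **Inputs.** Multiplier 70, seven variables and 490 participants with data per condition (protocol 9.2); planned recruitment of 490 per condition (synopsis); remission 43% vs 23% (protocol 9.2). The documents give no attrition rate for the cohort, no share with centralised pain, and no alpha for the cohort comparison. The values used below for these are assumptions.

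**Step 1: reproduce the plan's figure.** 70 x 7 = 490, which matches exactly. Implied allowance = 1 - (data needed / recruited) = 1 - 490/490 = 0.

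**Step 2: look for an allowance elsewhere.** The SAP (section 3.3) adjusts for 3.33% loss to follow-up, but this enters the calculation for the embedded randomised trial: 85 per group x (1 - 0.75²) = 37.19; 37.19/(1 - 0.033) rounds up to 39; 2 x 39 = 78. It plays no part in 490. For the feasibility study, protocol 9.2 treats attrition as something to be learned.

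**Step 3: effect of losing data on the seven variables.** Retained = 490 x (1 - d); ratio = retained / 7. Here d is the proportion without usable data at whichever time point the clustering uses. The 3.3% is the SAP's pilot rate and the 5% is the missing-data figure in SAP section 3.7. Both belong to the embedded trial at 3 months and are only illustrative for the cohort.

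| Assumed d | Retained of 490 | Per variable |
|---|---|---|
| 3.3% | 473.8, about 474 | 67.7 |
| 5% | 465.5, about 466 | 66.5 |
| 10% | 441 | 63.0 |
| 20% | 392 | 56.0 |

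**Step 4: which losses count.** Under protocol 7.4 the questionnaires are completed at baseline. Under 9.3 all collected data are used unless a withdrawing participant objects. A participant who is simply lost to follow-up therefore keeps baseline data in the analysis. Such a loss lowers the ratio only if the clustering uses follow-up data, and section 9.1 gives no time point. Missing baseline items and data removed on request lower it in either case.

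**Step 5: the 6-month remission comparison.** Power = Φ[(|p1 - p2| - 1.96 x SE0) / SE1], with SE0 from the pooled proportion and SE1 from the separate proportions, p1 = 0.43, p2 = 0.23 and two-sided alpha 0.05 (assumed). Take N = 392, which is 20% loss, and an assumed 20% with centralised pain. The groups are 313.6 and 78.4, the pooled proportion is 0.39, SE0 = 0.0616 and SE1 = 0.0551. Then (0.20 - 1.96 x 0.0616)/0.0551 = 1.44, and power is 0.925. Varying the assumed share:

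| Share with centralised pain | Power at N = 392 |
|---|---|
| 50% | 0.99 |
| 20% | 0.92 |
| 15% | 0.85 |
| 10% | 0.70 |

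**The case against.** The strongest reply is that 7.7 does not say which analysis it has in mind. The primary objective is the remission comparison. At 43% vs 23%, equal groups need 86 each, 172 in total, for 80% power (two-sided alpha 0.05 assumed), so 490 leaves room for loss there. That is correct as arithmetic. However, 9.2 does not derive 490 from that comparison and never presents the surplus as the attrition allowance, so the sentence in 7.7 still has no support in the text.

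A second reply is that attrition is not the same as deleted data. This stands, and it limits the consequence. A reader might infer that every participant lost to follow-up breaks the 70-per-variable rule, or that 10% to 20% of the data will go. The documents support neither. Collected data are kept unless the participant objects, the clustering time point is unstated, and no cohort loss rate is given.

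A third reply is that 70 per variable is a rule taken from a cited simulation, and nothing in the documents shows harm at 63 or 67 per variable. That also stands. The defect is that a stated property is absent. It is not shown that the clustering would fail.

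**Conclusion.** The inconsistency is real. As derived in 9.2, 490 contains no attrition allowance, and 7.7 says that it does. This conclusion needs no assumption.

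The size of the consequence does rest on assumptions. Over assumed losses of 3.3% to 20% in data on the seven variables, the ratio falls from 70 to between 67.7 and 56 per variable. If the clustering uses baseline data only, the relevant loss is limited to missing baseline items and data withdrawn on request.

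Two inferences about the primary comparison should be avoided. One is that it is underpowered because of this error. The other is that it is safe whatever the loss. Neither follows from the documents, because power depends on the share with centralised pain, which is not given. At N = 392 it runs from about 0.99 with equal groups to about 0.70 with 10% in the centralised-pain group.

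**What to change.** - **Section 7.7:** delete the attrition sentence, or reword it so that it no longer claims an allowance. If withdrawals are still not to be replaced, say so without giving attrition as the reason.
- **Section 9.2:** state that 490 per condition is 70 x 7 with no attrition allowance, and give the expected ratio per variable over a stated range of assumed loss: 67.7 at 3.3%, 66.5 at 5%, 63 at 10% and 56 at 20%.
- **Section 9.1:** have the sponsor specify which time point the cluster analysis uses. Baseline should be written in only if that is the plan.
- **Power:** if a statement about the 6-month DAS28 remission comparison is added, make it conditional on the share with centralised pain and show the range, including the less favourable shares.

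The cost is protocol wording and a slightly less favourable stated figure. No extra patients are needed. The synopsis gives a planned end date of 30 April 2025, so the main gain is accurate reporting of what 490 does and does not cover.

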7.8 Definition of End of Study

The end of study is the date of the last postal or online questionnaire/ telephone follow up of the last participant. If the participant has consented to be contacted for consideration of future studies, their name, contact details and musculoskeletal diagnosis will be retained on the research database for a period of 10 years after the end of the study.

8 SAFETY REPORTING

8.1 Definition of Serious Adverse Events

A serious adverse event is any untoward medical occurrence that:

- · results in death
- is life-threatening
- requires inpatient hospitalisation or prolongation of existing hospitalisation

- results in persistent or significant disability/incapacity
- consists of a congenital anomaly or birth defect.

Other 'important medical events' may also be considered serious if they jeopardise the participant or require an intervention to prevent one of the above consequences.

NOTE: The term "life-threatening" in the definition of "serious" refers to an event in which the participant was at risk of death at the time of the event; it does not refer to an event which hypothetically might have caused death if it were more severe.

8.2 Reporting Procedures for Serious Adverse Events

A serious adverse event (SAE) occurring to a participant should be reported to the REC that gave a favourable opinion of the study where in the opinion of the Chief Investigator the event was 'related' (resulted from administration of any of the research procedures) and 'unexpected' in relation to those procedures. Reports of related and unexpected SAEs should be submitted within 15 working days of the Chief Investigator becoming aware of the event, using the HRA report of serious adverse event form (see HRA website).

9 STATISTICS AND ANALYSIS

9.1 Description of Statistical Methods

Non-imaging data will be analysed using statistical software packages such as Stata. Initially descriptive statistics will be used to describe the results of demographic, disease activity and psychophysical assessments conducted across the difference conditions being studied. Statistical approaches used will include chi-squared tests of association, correlation, Student's t-test, and univariable linear regression models. Further analyses will explore whether pre-treatment pain characteristics, in particular the presence of centralises pain, predict response to treatment, measured by reduction in disease activity. This will be done using univariable regression analysis. We will also examine whether there are clusters or sub-groups of patients within the cohort, using data driven methods such as cluster analysis.

All imaging data will be analysed using standard methods within FSL (FMRIB Software Library). The first 5 subjects will be analysed as a first checkpoint to check data quality and other measures of quality. For the maladaptive learning assessments, the results from the online panel of games will be fitted from simulated data, based on pilot studies in patients/controls, for power analysis where parameters of interests will be highlighted with significant differences. The accuracy of model fitting will improve as more data is added i.e. the framework becomes more powerful as more data is added (intrinsic sustainability).

[figure not shown]

Figure 1. This illustrates what the output data looks like, shown here as the full parameter distributions, but can be simplified to basic summary statistics of the key learning parameters.

For the Sleep sub study, quantitative feasibility outcomes will be summarised descriptively. Qualitative data will be coded using inductive thematic analysis to examine participants' views and experiences of the recruitment process, intervention, and trial process, including MRI assessments. Themes that emerge will be discussed with the patient research partners.

9.2 Number of Participants

Previous work, using the ratio of tender to swollen joints as an indirect marker of central sensitization in patients with either RA or PSA, has shown that on average 43% of patients with low levels of likely central sensitization achieved remission (using DAS-28 remission criteria) compared to 23% in those with high levels of central sensitisation when being treated with either methotrexate or an anti-TNF agent. However a data simulation study showed that, for machine-learning methods, a sample size of 70 times the number of variables allows accurate identification of the data structure (36). Using the seven main variables of pain, fatigue, sleep disturbance, dyscognition, depression, anxiety and function, data for 490 participants, for each condition would be needed, including the feasibility study.

For the feasibility study 80 participants will be recruited in total, with 40 being assessed using MRI. Participants will be randomised on a 1:1 ratio to the intervention and standard care groups. This should provide a large enough sample to inform the practicalities of delivering dCBT-I, MRI assessments, and provide information on recruitment, uptake, and attrition, which will inform the design of the definitive trial. A moderate effect size (Cohen's d >0.3) would be sufficient to accept the result as worth investigating, in order to achieve a meaningful clinical benefit for patients, and in keeping with similar effects of CBT-I on cognitive outcomes in insomnia.

All participants in the Sleep sub-study will be invited to participate in the focus groups. However, it is envisioned that 18 (three groups of six participants) will take part, owing to the time commitment involved.

9.3 Analysis of Outcome Measures

All participant data will be used in the analysis of primary and secondary outcome measures, unless a participant has specified when withdrawing consent that they do not want data already collected to be analysed.

The participants will be divided into those with and without centralised pain, determined by the centralised sensitivity inventory. The difference between achieving remission will be assessed using the standardised DAS -28 criteria at 6 months, in line with the primary outcome measure. Regression analyses will be used to investigate any significant differences in outcome for the two groups, including univariate analyses followed by multivariate analyses adjusting for known predictors of outcome such as age, sex and baseline pain/disease activity severity.

Correlation analyses will be used to assess for any associations between different measures of central sensitization across the different musculoskeletal measures. This will be done for the group as a whole, as well for individual diagnoses to evaluate any differences in the relationships for the different conditions.

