4. OBJECTIVES AND OUTCOME MEASURES

Objectives	Outcome Measures	Timepoint(s) of evaluation of this outcome measure (if applicable)
Primary Objective To investigate whether patients with inflammatory arthritis and features of centrally driven pain have reduced chance of responding to treatment.	Percentage achieving Disease Activity Score <2.6. Other measures include Disease Activity Score reduction of >1.2; simple disease activity score <3.3; Clinical Disease Activity Index ≤2.8; American College of Rheumatology (ACR)/European League Against Rheumatism (EULAR) Boolean (28 tender joint count,28 swollen joint count, patient's global assessment (0−10 scale),CRP (mg/dL), all ≤1), modified DAPSA<4.	Baseline and at 3, 6 and 12 months after commencing therapy.
Secondary Objectives To investigate the features of centrally driven pain, detected through multi-modal assessment, in patients with a range of musculoskeletal conditions.	Scoring according to: Central Sensitivity Inventory, Fibromyalgia survey criteria, PainDETECT questionnaire alongside neuroimaging findings.	Prior to commencing therapy
To investigate whether patients with features of centrally driven pain have differences in NfL, inflammatory markers and genes which can prospectively identify prognostic factors for developing neuropathic pain, its persistence and/or its severity	Blood test	Baseline
To investigate whether digital CBT-I can improve quality of life and centrally driven symptoms in people with FM	SIQR, sleep actigraphy, sleep diary, online cognitive assessment, self-reported cognitive function (British Columbia Cognitive Complaints Inventory, BC-CCI) Neuroimaging (brain MRI)	Baseline, 12 weeks and 24 weeks Baseline and 12 weeks

To investigate the cost effectiveness of digital CBT-I	EQ-5D-5L Healthcare usage dairy	Baseline, 12 and 24 weeks
To determine barriers and facilitators to a definitive trial of CBT-I to alleviate symptoms in people with FM	Focus groups of participants	24 weeks
To investigate whether maladaptive learning in the brain plays a role in chronic musculoskeletal pain, and from this to predict treatment response in fibromyalgia patients		Baseline, 12 weeks
	Online games to include learning and decision-making, generalisation/ avoidance, motor decision-making, and prediction/metacognition tasks, and motor (movement) evaluation - videobased assessment measuring movement	
	during standardised physio-type exercises	

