7.4 Baseline Assessments

At the baseline assessment visit, participants will be asked to complete the clinical assessment and validated questionnaires described below. This will be done using REDCap, a secure web application online portal (redcap) where possible, either with the researcher present or independently according the participants preference. If required, a paper format will be used:

Assessment	Purpose
Clinical history	This will include disease duration, current and previous treatments including those for pain management specifically, and other past medical history
Disease activity score measure	Used in routine clinical practice to capture disease activity specific to a condition. For example: disease activity score-28 in rheumatoid arthritis, psoriatic response criteria in psoriatic arthritis, Bath ankylosing spondyloarthritis disease activity index in ankylosing spondyloarthritis, fibromyalgia impact questionnaire in fibromyalgia)
MRI safety questionnaire	Assess whether participant is safe to undergo MRI scanning
Euroqol-5D (EQ5D)/HAQ	Standardised measure of health-related quality of life
Musculoskeletal Health Questionnaire (MSK-HQ)	Supplementary measure of health status designed to be used across a range of musculoskeletal conditions in order to monitor progress over time and response to treatment
Beck depression and anxiety inventories	To assess and describe psychological comorbidity and its impact on symptoms and treatment response
PainDETECT questionnaire	To assess for features of neuropathic pain
Central sensitivity inventory	To indirectly assess centralised sensitisation
Insomnia severity index	To assess sleep disturbance, an important factor in pain experience

Fibromyalgia survey criteria	To assess for concurrent fibromyalgia in those with inflammatory arthritis, which may impact treatment outcome
Fibromyalgia Impact Questionnaire Revised*	To assess the overall impact of symptoms and
	quality of life in those with FM in Sleep sub-study
Chalder Fatigue Scale*	To assess self-reported fatigue in Sleep sub-study
Behavioural inhibition system/Behavioural	To assess reward responsiveness which may be
activation system (BIS/BAS) scale	impaired in chronic pain and impact on treatment responsiveness
The Multidimensional Assessment of	To assess interoception which may be impaired in
Interoceptive Awareness (MAIA)	patients with chronic pain
Locus of control	To quantify the degree to which participant feels

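### Protocol 9.3 tests the primary objective on a two-group CSI split with no stated cut-point; the CSI score itself should be the primary exposure, with one cut fixed in advance for a secondary comparison

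*Protocol*

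**What the plan says.** The primary outcome is binary. The Protocol synopsis gives it as "Percentage achieving Disease Activity Score <2.6, 6 months after commencing anti-rheumatic treatment". Section 9.3 defines the exposure: "The participants will be divided into those with and without centralised pain, determined by the centralised sensitivity inventory". It continues: "Regression analyses will be used to investigate any significant differences in outcome for the two groups", first unadjusted and then adjusted for known predictors, among them age, sex and the baseline severity of pain and disease activity.

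The baseline table in section 7.4 lists the CSI with the purpose "To indirectly assess centralised sensitisation". It gives no scoring range, threshold or severity band. The synopsis and sections 4, 9.1, 9.2 and 9.3 give no cut-point, no rule for choosing one and no expected share of participants above it.

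The correlations planned in 9.3 are between measures of central sensitisation, not between the CSI score and remission. Section 9.1 plans univariable regression of pain characteristics before treatment on response, measured as reduction in disease activity. It does not name the CSI score, and it is not the primary outcome. The SAP covers only the nested dCBT-I trial and does not mention the CSI.

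**The concern.** There are two separate problems, and writing down a cut-point solves only one.

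The first is the open choice. The primary odds ratio is not defined until someone decides where to cut the CSI. In an observational cohort, that decision can be taken by people who already hold both the CSI and the remission data.

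The second is loss of information. Within each group, participants with very different scores are treated as identical, so the estimate is less precise than the collected data allow. A cut fixed in advance does not recover this.

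At stake are the precision of the primary estimate, the chance of detecting an association smaller than the one quoted in 9.2, and the credibility of the primary p-value.

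**Working it through.** **1. The plan's own figure.** Section 9.2 takes 70 participants per variable and seven variables: 70 × 7 = 490 per condition. This reproduces exactly, but it is a rule for finding data structure, not a calculation for the CSI comparison. No power is stated for that comparison.

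**2. Inputs.** N = 490 (9.2). Remission is 43% and 23%: "on average 43% of patients with low levels of likely central sensitization achieved remission" and "compared to 23% in those with high levels of central sensitisation". These rates were obtained "using the ratio of tender to swollen joints as an indirect marker of central sensitization", so the CSI effect is not known. The following are assumptions because the Protocol does not state them for the cohort: two-sided 5% significance; the share s above the cut (varied); a roughly normal score; a linear logit; and 20% attrition where used.

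**3. Information kept by a cut.** For a normal score cut so that a share s lies above c = Φ⁻¹(1 − s), efficiency relative to the continuous score is φ(c)² / [s(1 − s)].

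| s | φ(c) | Efficiency | 490 cut participants carry the information of |
|---|---|---|---|
| 0.5 | 0.3989 | 0.637 | about 312 |
| 0.3 | 0.3477 | 0.576 | about 282 |
| 0.2 | 0.2800 | 0.490 | about 240 |

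A logistic model calibrated to 43% v 23% gives similar values: 0.69, 0.57 and 0.46.

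**4. Power of the two-group test at 43% v 23%.** Power = Φ[(0.20 − 1.96·SE₀)/SE₁], where SE₀ uses the pooled proportion and SE₁ the separate proportions. At s = 0.2 the groups are 392 and 98 and the pooled proportion is 0.39. Then SE₀ = 0.0551, SE₁ = 0.0493, and (0.20 − 0.1080)/0.0493 = 1.87, so power is 96.9%.

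| s | N = 490 | N = 392 (20% attrition, assumed) |
|---|---|---|
| 0.5 | 99.8% | 98.9% |
| 0.3 | 99.3% | 97.5% |
| 0.2 | 96.9% | 92.5% |

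**5. A smaller effect.** Assume half the difference, 38% v 28%, at a median split. For the cut, the log odds ratio is 0.455 and its variance is (8.49 + 9.92)/490, so z = √(490 × 0.455²/18.41) = 2.35 and power is Φ(2.35 − 1.96), about 65%. The relative efficiency of the cut in this model is 0.65, so for the continuous score z = 2.35/√0.65 = 2.91 and power is about 83%. With 20% above the cut the figures are about 45% and 77%.

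**6. Effect of an open cut.** Simulated null data (N = 490, 33% remission, no CSI effect), taking the smallest chi-squared p-value over the cuts tried:

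| Cuts tried | Chance of p < 0.05 |
|---|---|
| One, fixed in advance | 5% (nominal) |
| Two | about 9% |
| Five (30th to 70th percentile) | about 15% |
| Seven (20th to 80th percentile) | about 20% |
| Every cut between the 20th and 80th percentiles | about 35% |

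**7. If the relation is a step.** With 38% v 28% and a true step exactly at the median cut, simulated power is 66% for the cut and 47% for a linear term.

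**The case against.** **Power is ample.** A reader might infer from the efficiency figures that the study is underpowered. The documents do not support that. At the only rates they give, the two-group test has about 97% power or more for splits down to 20/80. What remains is that those rates belong to a joint-count ratio, so the CSI effect may be smaller, and that precision is lost whatever the power.

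**The objective is a group question.** It asks about patients with features of centrally driven pain, and the evidence in 9.2 is a high v low contrast. A per-SD odds ratio answers a related but different question, and a step at the cut would favour the split. This stands, and is the reason to keep the two-group comparison as a secondary analysis and to check for non-linearity.

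**No search for a cut is planned.** This also stands. A reader might take the 35% as the expected error rate. It is the extreme of a range set by how many cuts are tried, and nothing in the Protocol suggests that several would be.

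**An established cut may be intended.** Possibly, but neither document says so. Stating it would close the open choice without recovering the information.

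**Confounding.** A reader might infer that splitting the CSI leaves residual confounding by baseline severity. That would follow from cutting severity, which 9.3 does not propose. In null simulations with severity kept continuous (CSI–severity correlation of 0.5, assumed), the binary CSI rejected in about 5% of runs.

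**Conclusion.** The point holds as a matter of analysis choice. The primary exposure is a dichotomised score with no cut-point in either document, and the score is never analysed against remission. Under a roughly normal score and a linear logit, the split discards about 36% of the information at the median and 51% at 20/80.

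This is neither a finding of low power at 43% v 23% nor evidence that a cut will be chosen from the data. The consequences are a less precise primary estimate, a real loss of power if the CSI effect is smaller than the quoted one (about 83% v 65% under the assumed half-size difference at a median split), and a primary result that is undefined until the cut is chosen. The size of the loss depends on the shape of the relation and on the share above the cut, and the documents give neither.

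**What to change.** Before outcome data are examined, amend section 9.3 as follows.

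- **Primary model:** logistic regression of DAS28 remission at 6 months on continuous baseline CSI, reported as an odds ratio per SD. Include a pre-specified spline check of non-linearity. Adjust for age, sex and the baseline severity of both pain and disease activity, as 9.3 already lists.
- **Secondary analysis:** the comparison of those with and without centralised pain, at one CSI cut-point written down at the same time, with the remission percentage in each group.

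No new data, visits or participants are needed, because the CSI is already collected at baseline. The cost is Protocol wording and, if the change is classed as substantial, the approval described in section 12.4. The planned study period in the synopsis ends on 30 April 2025, so the amendment should record whether any outcome data had been examined when the model and cut were fixed. A per-SD odds ratio is less direct to read than two percentages, and a linear term loses power if the true relation is a step at the cut. The secondary comparison covers both, and the spline check helps with the second.
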